#### **10.4.1.4 Other Analyses**

Child Health Questionnaire (CHQ-PF50; health-related quality of life) response will also be summarized at each visit, and will be used in exploratory analyses. The analyses of inactive disease assessment, uveitis assessment, swollen joint count and tender joint count will be provided. For patients being enrolled from AbbVie clinical Study DE038 or

Study M10-444, baseline will be defined as the last non-missing observation on or before the date of enrollment in the registry since these assessments were not collected in Study DE038 or not collected in Study M10-444 or not collected in both studies. Details will be provided in the SAP.

#### **10.4.2 Analysis of Effectiveness for Intermittent Treatment with Humira**

The objective for analyses of pre-TI and post-TI effectiveness is to determine whether patients can recover pre-TI effectiveness once Humira treatment is reinitiated after the treatment interruption. The analytic approach is based on results from the polyarticular JIA development program which demonstrated that most of the efficacy of Humira in polyarticular JIA is achieved within 12 weeks after initiating treatment.

Effectiveness analyses will be performed only with patients who complete at least 12 weeks of treatment before the TI. Patients need to have at least one visit collecting effectiveness data after the TI. Effectiveness variables will be summarized at 12 weeks after the first dose of the pre TI period and compared to the results at 12 weeks after the first dose of the post-TI period.

If effectiveness results are not available at 12 weeks post-TI, then:

For patients whose last effectiveness assessment is before Week 12 of the post-TI period, the last post-TI effectiveness assessment prior to discontinuation will be carried forward.

For patients whose last effectiveness assessment is after Week 12 of the post-TI period, the first post-TI effectiveness assessment after Week 12 will be used.

A comparison of the best response (measured by PedACR 30) in the same patient before and after TI will be provided.

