information. Since this is an observational registry conforming to usual clinical practice, data will be collected from patient visits that most closely correspond to the protocol intervals in [Table 1](#). Months 1 and 3 (not required for patients who participated previously in an AbbVie sponsored Humira study), and Month 6 followed by routine office visits every 6 months through Year 5. For example, if a patient visits the investigator at Month 5, this is close to the protocol-defined 6-month visit, so data can be collected for this visit. If the same patient unexpectedly returns for a visit the investigator's site at a date closer to the 6 month visit, no further effectiveness data needs to be collected since the data was previously collected. Safety data that meets the criteria for collection should be collected regardless of protocol-defined registry visits.

For collection of Safety data, see [Figure 1](#) and [Figure 2](#).

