**Table 2. Definition of Pre-TI and Post-TI Periods**

	Pre-TI Period	Post-TI Period
Start	First injection of the registry	Day of first injection following the longest TI
End	70 days following the last injection before the longest TI	70 days following registry completion/stop of participation

The preceding summaries do not distinguish between the same adverse events experienced by the same patients pre-TI and post-TI from the same adverse events experienced by different patients pre-TI and post-TI. Therefore, a third summary will evaluate the proportions of patients who report onset of the same adverse event pre-TI and post-TI, patients who report onset only pre-TI, patients who report onset only post-TI, and patients who do not report the event in either period.

For each TI experienced by 1% of patients and for each SAE and Adverse Event of Special Interest, the number and percent of patients who have the event or not before the TI and after the TI will be summarized as shown in [Table 3](#). This assessment will provide information about whether same or different patients experience the adverse pre-TI and post-TI.

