### **10.4 Effectiveness Analyses**

Effectiveness data will be analyzed as observed, as this is an observational registry. The number of patients with non-missing baseline and visit values, baseline mean, visit mean, mean and standard deviation of change from baseline will be provided for continuous variables. Counts and percentages will be provided for categorical variables.

The effectiveness data will be summarized for the All Treated Patient Population (from the first dose in the registry).

The baseline measurements used in the effectiveness tables for this registry are measurements on or before the first day in the registry, except that for the subjects who are rolled over from a prior AbbVie study (Study DE038 and Study M10-444), the baseline measurements will be the baseline measurements collected in the prior study (Study DE038 and Study M10-444).

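### The Week 12 before/after-interruption effectiveness comparison (Section 10.4.2) fills missing values on the post-TI side only and requires no pre-TI value, so its two summaries can rest on non-identical patient sets

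*Supplement*

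**What the plan says.** Section 10.4.2 gives the aim as to "determine whether patients can recover pre-TI effectiveness once Humira treatment is reinitiated after the treatment interruption". Its provisions are:

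- **Eligibility before the TI:** "Effectiveness analyses will be performed only with patients who complete at least 12 weeks of treatment before the TI". This is a condition on treatment, not on having been assessed.
- **Eligibility after the TI:** "Patients need to have at least one visit collecting effectiveness data after the TI".
- **Comparison:** "Effectiveness variables will be summarized at 12 weeks after the first dose of the pre TI period and compared to the results". The comparator is the corresponding Week 12 once Humira has been restarted.
- **Missing values:** the rule opens "If effectiveness results are not available at 12 weeks post-TI, then". If a patient's last assessment precedes post-TI Week 12, it is carried forward. If it comes later, the first assessment after Week 12 is used. There is no matching rule for pre-TI Week 12.
- **Same-patient analysis:** a within-patient comparison is stated for best PedACR30 response only.

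Four other places bear on this:

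- Section 10.4 analyses effectiveness as observed. For roll-overs from DE038 and M10-444, "the baseline measurements will be the baseline measurements collected in the prior study".
- Section 6.6 lists visits at "Months 1 and 3 (not required for patients who participated previously in an AbbVie sponsored Humira study"), then Month 6 and every 6 months through Year 5. Table 1, note c, agrees.
- Table 2 in Section 10.3.4, written for the safety summaries, starts the pre-TI period at "First injection of the registry".
- Section 10.4.1.4 gives CHQ-PF50, inactive disease, uveitis, and swollen and tender joint counts a registry-entry baseline for roll-overs.

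**The concern.** Recovery is a question about the same patient at two times. The written rules supply a post-TI value for every eligible patient but leave the pre-TI value to chance. Part of any difference between the two summaries can then come from who is counted rather than from what happened to anyone.

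The gap is unlikely to be random. Roll-overs have no required visit near pre-TI Week 12, and for core-set change and PedACR they are measured against the prior study's baseline. Other patients are measured against a value on or before the first registry day, and Section 6.1.1 lets them enter up to 24 months after starting Humira. The two groups' changes from baseline are therefore not on the same footing, and the mix of patients matters.

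The impact of interruptions on effectiveness is part of the secondary objective (Section 5.0). The protocol also recognises the issue for safety: Section 10.3.4 notes that aggregate before/after summaries cannot separate the same patients from different ones, and adds a paired shift table (Table 3). The Week 12 effectiveness comparison has no such addition.

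**Working it through.** The documents state no figure for this analysis, so there is none to reproduce. The check has two parts.

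**1. Who has a value on each side**

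Inputs are the visit schedule (Section 6.6; Table 1, note c), the TI definition of more than 70 days without an injection (Section 10.1), and the Table 2 start of the pre-TI period, assumed to apply here too.

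- Pre-TI Week 12 is day 12 × 7 = 84.
- New patients have a Month 3 visit at about day 365.25/4 = 91, one week later.
- Roll-overs have enrollment and then Month 6, at about day 365.25/2 = 183. That is 183 − 84 = 99 days after Week 12.
- The earliest restart for an eligible patient is about day 84 + 71 = 155, so post-TI Week 12 is at about day 155 + 84 = 239 or later. By then everyone is on 6-monthly visits.
- If restart falls uniformly within the 6-month cycle (an assumption), a scheduled visit lies within 2 weeks of post-TI Week 12 for 28/182.6 = 15% of patients, and within 4 weeks for 56/182.6 = 31%.
- When the next scheduled visit is used, it falls on average at Week 12 + 13 = 25, and at the latest at about Week 38.

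So most post-TI values are likely to come from the substitution rule, and every eligible patient receives one. The pre-TI summary holds only patients with an observed Week 12 value. The pre-TI contributors are nested in the post-TI set.

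**2. Size of the artefact when no patient changes**

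Let q be the share of eligible patients with no pre-TI value, μ_A the mean of those who have one, and μ_B the mean of those who do not.

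- Pre-TI summary: μ_A
- Post-TI summary: (1 − q)μ_A + qμ_B
- Difference: q(μ_B − μ_A) = q × D

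Example with q = 0.30, μ_A = 25 mm and μ_B = 15 mm: pre-TI 25; post-TI 0.7 × 25 + 0.3 × 15 = 22. The apparent gain is 3 mm, with nobody changed.

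The documents give neither q nor D. The range below is assumed. Its upper share is 228/500 = 0.456: all patients enrolled in three earlier JIA studies (Section 3.0) over the planned Humira arm (Section 6.3). That is an outer bound on roll-overs in the arm, not an estimate of q among interrupted patients.

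| q | D = 5 mm | D = 10 mm |
|---|---|---|
| 0.10 | 0.5 | 1.0 |
| 0.20 | 1.0 | 2.0 |
| 0.30 | 1.5 | 3.0 |
| 0.456 | 2.3 | 4.6 |

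A simulation with no within-patient change matched q × D to within 0.06 mm. Restricted to patients with both values, the mean change was between −0.03 and +0.02 mm.

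**The case against.** The strongest reply is that Section 10.4.2 never says the comparison is unpaired. It defines one eligible cohort and asks whether those patients recover. Pairing, denominators and visit windows are commonly left to an SAP, the protocol refers to one (Section 10.4.1.4), and none is shown. This stands in part: the text is silent on pairing, and two separate summaries is an inference from its wording. It does not dispose of the point, because the one-sided substitution rule and the one-sided visit requirement are written in the protocol, and Section 10.4.2 itself defers nothing to an SAP.

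Other limits also stand:

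- The two sides do not hold different patients; one set is contained in the other.
- Table 2 belongs to the safety summaries, and Section 10.4.2 does not define the first pre-TI dose. A Month 3 visit is not required for roll-overs, but it may still occur.
- The baseline argument does not reach the Section 10.4.1.4 variables. It also does not reach any variable summarized as a level rather than a change.
- The best PedACR30 comparison is already within-patient. It covers one binary measure and not the Week 12 time point.

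A reader might infer that the analysis is bound to show recovery, or that it carries an inflated false-positive rate or a quantifiable loss of power. The documents do not support either reading. The direction depends on how roll-overs differ from the rest, which is not given. Section 10.4 plans descriptive statistics and Section 10.4.2 names no test, so there is no error rate or power to evaluate.

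**Conclusion.** The point holds as a defect in the written rule: followed literally, it lets the pre-TI and post-TI Week 12 summaries rest on non-identical patient sets. The identity q × D needs no distributional assumption. Its value here, about 0.5 to 4.6 mm on a 100 mm VAS, rests entirely on the assumed shares and gaps and could lie outside that range.

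That roll-overs are the main group missing before the TI is likely rather than certain, since it depends on Table 2 applying to this analysis. For core-set change and PedACR, the differing baselines mean that the mix of patients could distort the comparison in either direction. The analysis is descriptive and serves a secondary objective. The change should still be made: the question is one the registry sets out to answer, and as written a reader could not separate recovery from a change in who was counted.

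**What to change.** Amend Section 10.4.2, or settle it in the SAP before the analysis is run, as follows:

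1. Restrict the Week 12 comparison to patients with an effectiveness value on both sides.
2. Define the first dose of the pre-TI period for this analysis. Apply the same visit-selection rule to pre-TI and post-TI Week 12, using only values before the TI starts on the pre-TI side. State whether an enrollment value may be carried forward.
3. For continuous variables, report the mean within-patient difference with its 95% confidence interval. For PedACR and inactive disease, report the paired 2×2 table.
4. State the number excluded for lack of a pre-TI value, by roll-over status.

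The cost is a few sentences and the re-programming of one set of tables, with no new data. The drawback is a smaller analysed set. The shared visit rule limits the loss: a roll-over whose TI starts after Month 6 keeps a pre-TI value at about Week 183/7 = 26, close to the average Week 25 expected after the TI when the next scheduled visit is used.

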##### **10.4.1.1 Definition PedACR30 Response**

A PedACR30 response will be defined as:

30% improvement in at least three of the six polyarticular JIA core set variables and

30% worsening in not more than one of the six remaining polyarticular JIA core set criteria.

The percent change will be calculated as:

$$100 \times (\text{Value} - \text{Baseline}) / \text{Baseline}$$

Improvement of a core set of variables by ≥ 30% is defined as a percent change from Baseline less than equal to –30% and worsening of a core set of variables by ≥ 30% is defined as a percent change from Baseline greater than or equal to 30%.

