#### **10.4.1.2 Definition of PedACR 50 and PedACR 70 and PedACR 90 Response**

PedACR50, 70 and 90 levels of response will be defined by using improvement percentages of 50, 70 and 90, respectively, in at least 3 of the 6 core set parameters with worsening of 30% or more in no more than 1 of the 6 core set parameters. The effectiveness individual indicators and the PedACR30/50/70/90 response will be summarized descriptively at each registry time point ([Figure 1](#) and [Figure 2](#)).

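### The same-patient comparison of best response before and after a treatment interruption is cut at PedACR30, so it cannot show whether patients regain a higher level they had reached before

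*Supplement*

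**What the plan says.** Protocol section 10.4.2 gives the aim of the pre-TI and post-TI effectiveness analyses: to "determine whether patients can recover pre-TI effectiveness once Humira treatment is reinitiated after the treatment interruption". It then plans two things.

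1. A 12-week comparison: "Effectiveness variables will be summarized at 12 weeks after the first dose of the pre TI period and compared to the results at 12 weeks", counted from the dose that restarts Humira. Patients need at least 12 weeks of treatment before the TI and at least one effectiveness visit after it. Rules are given for a missing post-TI Week 12 value. The variables are not listed, and the comparison is not stated to be within patient.
2. A within-patient comparison: "A comparison of the best response (measured by PedACR 30) in the same patient before and after TI will be provided".

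Section 10.4.1.1 sets the PedACR30 threshold as "30% improvement in at least three of the six polyarticular JIA core set variables and" 30% worsening in no more than one of the others. Section 10.4.1.2 adds the higher levels: "PedACR50, 70 and 90 levels of response will be defined by using improvement percentages of 50, 70 and 90". It also states that the "PedACR30/50/70/90 response will be summarized descriptively at each registry time point". Nothing in the protocol uses PedACR50, 70 or 90 in the same-patient comparison. No section defines what counts as recovered, and no test is named. No separate SAP is shown.

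**The concern.** The aim concerns each patient's own earlier level. A patient who had PedACR90 before the TI has recovered only on getting back to about that level. The planned paired comparison asks something weaker: was PedACR30 met at some visit before the TI, and again at some visit after it? Because it takes the best response in each period, one qualifying visit on each side is enough.

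At stake is the most direct evidence on the question. The effect of interruptions on effectiveness is part of the secondary objective in section 5.0. A reader of the planned table could see most patients as responders before and after, and could not tell whether they had kept a high response or slipped to a modest one. The higher levels are already derived, and the protocol gives no reason for leaving them out here.

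**Working it through.** The protocol states no figure for this analysis, so there is none to reproduce. The check has three parts.

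**1. Which declines the cut can show.** Inputs: the levels in sections 10.4.1.1 and 10.4.1.2, ordered none < 30 < 50 < 70 < 90.
- Possible declines from a higher to a lower level: 5 × 4 / 2 = 10.
- Visible after a cut at PedACR30: only those ending at none, from 30, 50, 70 or 90, which is 4.
- Hidden: 10 − 4 = 6, namely 90→70, 90→50, 90→30, 70→50, 70→30 and 50→30.

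This counts category pairs, not patients, and needs no distributional assumption.

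**2. A constructed patient.** Assumed baseline: physician global 60 mm, parent global 60 mm, 20 active joints, 15 joints with limitation of motion, DICHAQ 1.5, ESR or CRP 30. The best pre-TI value of each variable is taken as 0.099 × baseline and the best post-TI value as 0.69 × baseline. Fractional joint counts are accepted for the illustration.
- Percent change by the section 10.4.1.1 formula, 100 × (value − baseline) / baseline: −90.1% before TI and −31% after.

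| Measure | Before TI | After TI |
|---|---|---|
| PedACR30 | yes | yes |
| PedACR50 | yes | no |
| PedACR70 | yes | no |
| PedACR90 | yes | no |

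- JADAS without the ESR/CRP term: baseline 6 + 6 + 20 = 32.0; before TI 0.099 × 32 = 3.2; after TI 0.69 × 32 = 22.1.

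The planned comparison records no change for a patient who has lost most of the improvement.

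**3. Possible size, by assumption only.** The protocol gives no response distribution around a TI and no expected number of patients with one. Assume a bivariate normal latent response with within-patient correlation 0.5, cut into the five levels, and a uniform loss after TI.
- Pre-TI PedACR30/50/70/90 of 90/80/65/45% and a loss of 0.5 SD: PedACR30 falls from 90% to 78%, PedACR90 from 45% to 27%.
- Across losses of 0.3 to 0.5 SD and a pre-TI PedACR30 of 90% or 80% (the latter with 80/65/50/30%), about 53 to 71% of patients who drop at least one level are still PedACR30 responders.
- If tests were applied to 50 patients in the first scenario, an exact McNemar test on PedACR30 would have about 33% power and a signed-rank test on the level reached about 84%. Over 30 to 80 patients, 0.3 to 0.5 SD and a start of 80 or 90%, the gap is about 18 to 51 points.
- The gap shrinks as pre-TI PedACR30 falls: to at most about 24 points at an assumed 60%, and about 17 at 40%.

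**The case against.** The strongest reply is that section 10.4.2 does not rest on this one line. The 12-week comparison comes first, and the effectiveness variables in section 6.7.1 include graded measures: pain and global VAS scores, DICHAQ, CHQ-PF50 and joint counts. A fall from PedACR90 to PedACR30 would move these on average, and the entry conditions mean largely the same patients supply both sides. This stands against any reading that recovery is judged by PedACR30 alone. It does not mend the paired comparison, because the 12-week analysis is not stated to be paired, does not name its variables and looks at a fixed time rather than best response.

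Three other inferences a reader might draw are not supported.
- **That such a patient counts as fully recovered.** The protocol sets no recovery criterion. The patient would appear as a responder before and after, no more.
- **That PedACR30 is at its ceiling before the TI.** Under section 10.4, patients who did not roll over from a prior study have their baseline on or before the first registry day, and section 6.1.1 lets them enter up to 24 months after starting Humira. For those already treated, change is measured from an on-treatment value, so PedACR30 need not be near 90%.
- **That the analysis is underpowered, or the subgroup small.** Section 10.4 is descriptive, no test is planned, and no number of patients with a TI is given.

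It may also be said that such detail belongs in a SAP. A SAP may add levels, but the protocol names PedACR30 explicitly, so the line is better corrected where it stands.

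**Conclusion.** The point holds in a limited form. The only comparison stated to be within the same patient cannot show whether a PedACR50, 70 or 90 responder regains that level, although that is the stated aim and the levels are already derived. The cut hides 6 of 10 possible declines; this follows from the definitions alone.

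The number of patients concerned cannot be obtained from the protocol. The simulated shares and power figures rest on assumed response rates, correlation and loss, and serve only as illustration. The material does not show that the section's overall conclusion would be biased towards recovery. The change is worth making because it answers the stated question directly at almost no cost.

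**What to change.** In section 10.4.2, replace the PedACR30 criterion in the same-patient comparison with the highest PedACR level reached in each period (none/30/50/70/90). Present it as a 5 × 5 pre/post-TI shift table with the percentage of patients who regain at least their pre-TI level. State the denominator for that percentage, since a patient with no response before the TI meets the condition automatically. Keep PedACR30 as one row. A paired signed-rank comparison is optional, as the plan is descriptive.

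The cost is one line of wording and one table. No new data are needed, and section 10.3.4 already uses a pre/post-TI shift table for adverse events (Table 3).

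### The best-PedACR30 comparison before and after interruption sets no common window, so it partly measures how many visits fall on each side

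*Supplement*

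**What the plan says.** Section 10.4.2 states its aim as "to determine whether patients can recover pre-TI effectiveness once Humira treatment is reinitiated". Its main analysis compares effectiveness 12 weeks after the first dose of the pre-TI period with effectiveness 12 weeks after the first dose of the post-TI period, with substitution rules when the post-TI value is missing. It then adds one sentence: "A comparison of the best response (measured by PedACR 30) in the same patient before and after TI will be provided".

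That sentence does not define best response, set a window or match visits. The section sets only minimum requirements. On the pre-TI side, "Effectiveness analyses will be performed only with patients who complete at least 12 weeks of treatment before the TI"; on the post-TI side, one effectiveness visit is enough.

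Section 10.4.2 uses the terms pre-TI and post-TI period without defining them. The only definition is Table 2 in Section 10.3.4, a safety section:

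- **Pre-TI:** from "First injection of the registry" to "70 days following the last injection before the longest TI".
- **Post-TI:** from "Day of first injection following the longest TI" to "70 days following registry completion/stop of participation".

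Section 10.4.1.1 defines PedACR30 as met or not met. Sections 6.6 and 6.6.6 place effectiveness visits at Months 1 and 3 (not required for patients from earlier sponsor studies), Month 6, and every 6 months through Year 5. Section 10.4 analyses effectiveness as observed.

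**The concern.** For a yes/no measure, best response in a period means a response at one or more visits. That probability rises with the number of visits even when the chance of response at each visit stays the same. Under Table 2, both period lengths depend on when the longest interruption falls and when the patient leaves. The early schedule adds Months 1 and 3 to the pre-TI side only.

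A patient who interrupts late has many chances to respond before and few after; an early interruption does the opposite. The output could therefore suggest lost response, or a gain, when nothing has changed, and a reader could not separate this from true recovery. The effect of interruptions on effectiveness is part of the registry's secondary objective in Section 5.0.

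**Working it through.** The plan gives no figure for this output, so there is none to reproduce. The check asks what the comparison would show under full recovery, with the same per-visit response on both sides.

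**Inputs from the protocol.** Visits at Months 1, 3, 6, 12, ..., 60 (12 for a new patient, 10 for a rollover patient). Table 2 periods, with visits stopping at Month 60. Interruption of more than 70 days with restart within 1 year of the last injection (Section 10.1). At least 12 weeks of treatment before and one visit after. About 68% dropout (Section 10.6).

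**Assumptions, not in the protocol.** Per-visit response p of 0.5 to 0.7; within-patient correlation ρ of 0.3 to 0.7, with 0 shown for reference; one interruption per patient; every scheduled visit assessed.

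**Formula.** For k independent visits, P(any response) = 1 − (1 − p)^k. With correlation (beta-binomial), a = p(1 − ρ)/ρ, b = (1 − p)(1 − ρ)/ρ, and P(any response) = 1 − ∏ (b + i)/(a + b + i) for i = 0, ..., k − 1.

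Example with p = 0.5 and ρ = 0.5, so a = b = 0.5. For k = 2: 1 − 0.5 × 0.75 = 0.625. For k = 9 the product is 0.185, giving 0.815.

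**Single patterns**, new patient, p = 0.5, pre vs post (%):

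| Last dose / restart (month) | Visits pre / post | ρ = 0 | ρ = 0.3 | ρ = 0.5 | ρ = 0.7 |
|---|---|---|---|---|---|
| 6 / 12 | 3 / 8 | 87.5 vs 99.6 | 76.3 vs 90.4 | 68.8 vs 80.4 | 61.2 vs 68.8 |
| 24 / 30 | 6 / 5 | 98.4 vs 96.9 | 87.3 vs 84.9 | 77.4 vs 75.4 | 66.8 vs 65.4 |
| 42 / 48 | 9 / 2 | 99.8 vs 75.0 | 91.5 vs 67.5 | 81.5 vs 62.5 | 69.6 vs 57.5 |

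At p = 0.7 and ρ = 0.5, 9 vs 2 visits gives 92.9% vs 80.5%.

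**Average over patients.** Simulation of 200,000 new patients: last dose before the interruption uniform from 12 weeks to Month 57, time to restart uniform from 71 days to 12 months, at least one later visit required. Without dropout, the mean is 6.5 visits before and 4.7 after, and 5% of patients have equal counts. With exponential dropout reaching 68% by Month 60, the means are 5.9 and 4.1, and 7% have equal counts.

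| p | ρ | No dropout: pre → post (fall) | 68% dropout: pre → post (fall) |
|---|---|---|---|
| 0.5 | 0.3 | 86.5 → 79.0 (7.5) | 84.9 → 75.6 (9.3) |
| 0.5 | 0.5 | 77.1 → 71.3 (5.8) | 75.8 → 68.8 (7.0) |
| 0.5 | 0.7 | 66.7 → 63.0 (3.7) | 65.8 → 61.4 (4.4) |
| 0.7 | 0.3 | 95.5 → 90.8 (4.7) | 94.8 → 88.7 (6.1) |
| 0.7 | 0.5 | 90.4 → 86.3 (4.1) | 89.5 → 84.4 (5.1) |
| 0.7 | 0.7 | 83.0 → 80.3 (2.7) | 82.5 → 79.1 (3.4) |

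**After matching.** With 2 visits on each side and p = 0.5, both sides give 75.0% (independent) or 62.5% (ρ = 0.5). The artefact is zero.

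**The case against.** **The Table 2 link is inferred.** Section 10.4.2 does not cite Table 2, whose end points are adverse-event windows. Its post-TI end can run to Year 10, whereas effectiveness collection stops at Year 5. This stands: the whole-period reading is plausible, because no other definition exists, but it is not stated.

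**An analysis plan could set the window.** None is among the documents, and derivation detail is often left to one. This stands in part. Section 10.4.1.4 expressly defers details to an analysis plan, but Section 10.4.2 does not. What it does commit to, best response on each side, misleads if followed as written.

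**The main recovery analysis is sound on this point.** The Week 12 comparison is anchored to first dose on both sides and has no any-visit effect. The best-response sentence is an untested descriptive addition. This stands and limits the weight of the point.

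**The size is easily overstated.** From one example, 6 vs 2 visits at 60% response, a reader might infer a distortion of 13 to 16 points: 1 − 0.4^6 = 99.6% vs 1 − 0.4^2 = 84.0% if independent, and 84.9% vs 72.0% at correlation 0.5. That is one visit pattern. Zero correlation is implausible for repeated measures in the same child, and at correlation 0.8 the same example gives 70.6% vs 64.8%. Early and late interruptions also partly cancel. Nor does the longer period always win: at p = 0.5 and ρ = 0.5 without dropout, 12.0% of patients change from responder to non-responder and 6.3% the other way, so 81.7% tie.

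**Conclusion.** The point holds as a minor one. Read with the Table 2 periods, the best-response comparison favours the side with more visits when nothing has changed. Over the assumed ranges, the average spurious fall is 2.7 to 7.5 percentage points without dropout and 3.4 to 9.3 with it. It shrinks as within-patient correlation rises but was not zero at any average tried. Late interruptions show a larger apparent loss, and early ones an apparent gain.

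These sizes rest on the assumed response rate, correlation and interruption timing, none of which the protocol gives, and on Table 2 being the intended window. A reader might infer that the whole recovery analysis is invalid, or that it is bound to show loss. The documents support neither: the Week 12 comparison does not share this fault, and the direction depends on when interruptions occur.

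**What to change.** Amend the sentence in Section 10.4.2 so that best response is derived on both sides over windows of equal length, measured from the first dose of each period, with the same number of assessments per patient. Equal length alone is not enough, because new patients have the extra Month 1 and Month 3 visits only at the start. Alternatively, drop this output and rely on the Week 12 comparison.

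Comparing the last on-drug visit before the interruption with the first visit at least 12 weeks after restart is not a good substitute. Time on drug would differ between the sides, and the pre-TI value would be selected on disease state around stopping.

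The cost is one sentence and minor programming. Patients without assessments in the matched window leave this output, and later visits are not used in it.
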